4.2. Exclusion Criteria

Participants with any of the following characteristics/conditions will not be included in the study:

1. Anti-AAV-Spark100 neutralizing antibody titer above the established threshold performed by a central laboratory during screening in hemophilia B participants or Anti-AAV6 neutralizing antibody titer above the established threshold performed by a central laboratory during screening in hemophilia A participants.

2. Lack of participant compliance with documentation of bleeds and/or prophylaxis replacement therapy administration.
3. If there is no documentation regarding hepatitis status, as defined below, within the last 12 months prior to screening for hepatitis B and 6 months prior to screening for hepatitis C, then participants will be required to have the following hepatitis testing performed at screening:

- a. **Hepatitis B screening (acute and chronic):**

HBsAg (also referred to as Hepatitis B surface antigen),
HBV-DNA viral assay (also referred to as a nucleic acid test for Hepatitis B virus DNA), and Anti-HBc (also referred to as Total Hepatitis B core antibody).

- a. **Hepatitis B screening (acute and chronic):**
- A participant is not eligible if either HbsAg is positive or HBV-DNA is positive/detectable.
- Anti-HBc must be obtained in all participants for determination of whether the participant had prior hepatitis B. If the anti-HBc is positive and both HBsAg and HBV DNA are negative this would be consistent with a *prior* infection and the participant would be eligible for the study. Anti-HBc must be obtained in all participants to discriminate between those with no prior hepatitis B and those with prior infection in the event of reactivation. FDA has noted reactivation of hepatitis B virus exists.
- One documented negative HBV-DNA viral load is sufficient to assess eligibility. A participant who is currently undergoing anti-viral therapy for hepatitis B is not eligible.

- b. **Hepatitis C (acute or chronic):**

- b. **Hepatitis C (acute or chronic):**
- A participant who is currently undergoing anti-viral therapy for chronic hepatitis C is not eligible.
- Participants treated with anti-viral therapy for chronic hepatitis C, must have completed anti-viral therapy at least 6 months prior to screening and have a negative HCV-RNA at least 6 months prior to screening.

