5.2. Participant Compliance

It is recommended that the study site will review participant compliance on a weekly basis but at a minimum monthly to align with the interim phone call to confirm participant compliance with electronic diary entry. The investigator, along with the sponsor will determine if a participant should be withdrawn from the study due to a participant's non-compliance which could be damaging to the study results or the participant's best

interests. Participants who are withdrawn for non-compliance or any other reason will have an Early Termination Visit.

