9. DATA ANALYSIS/STATISTICAL METHODS

Detailed methodology for summary and statistical analyses of the data collected in this study is outlined here and further detailed in a statistical analysis plan (SAP), which will be maintained by the sponsor. The SAP may modify what is outlined in the protocol where appropriate; however, any major modifications of the primary endpoint definitions or their analyses will also be reflected in a protocol amendment.

All data analyses will be performed separately for each population (hemophilia A and hemophilia B). There will be no joint analysis done that includes both populations together outside of the exploratory endpoint of neutralizing antibody positivity rates.

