9.2. Efficacy Analysis

All participants that signed the ICD, were subsequently identified as nAb negative (negative for circulating IgG antibody to AAV-Spark100, or negative for circulating IgG antibody to AAV6) and who participated in the prospective data collection phase as part of their usual healthcare setting will be included in the efficacy analysis set. The cohort of hemophilia B and hemophilia A participants will be analyzed separately.

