4.2. Efficacy Analysis Set

All participants in the full analysis set who were subsequently identified as nAb negative (negative for nAb to AAV-Spark100 for the hemophilia B cohort, or negative for nAb to AAV6 for the hemophilia A cohort), fulfilled the inclusion/exclusion criteria and who participated in the prospective data collection phase as part of their usual healthcare setting will be included in the efficacy analysis set (Groups B1, B2 and B3 in Figure 2).

Note: With regard to exclusion criterion 2 (Protocol Amendment 8, Section 4.2), any participant with more than 120 days of follow-up and for which the maximum number of days between 2 consecutive FVIII/FIX infusion records represents more than 25% of their follow-up duration will be considered non-compliant with documentation of bleeds and/or prophylaxis replacement therapy administration and will be excluded from the efficacy analysis set.

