6. ANALYSES AND SUMMARIES

6.1. Primary Endpoint(s)

6.1.1. Annualized Bleeding Rate

The primary endpoint listed in the protocol is the annualized bleeding rate (ABR; treated and total).

ABR during the prospective data collection period

Annualized bleeding rate during the prospective data collection period will be summarized using descriptive statistics (ie, n, mean, standard deviation, median, Q1, Q3, minimum, maximum) by cohort. The ABR will be summarized for the efficacy analysis set, the per-protocol analysis set, and the PA#5 analysis set.

ABR during the retrospective data collection period

Annualized bleeding rate during the retrospective data collection period will be summarized using descriptive statistics. The ABR will be summarized for the PA#5 analysis set.

ABR from the combined the retrospective and prospective data collection period

Annualized bleeding rate from the combined retrospective and prospective data collection period will be summarized using descriptive statistics. The ABR will be summarized for the PA#5 analysis set.

ABR will be listed in a data listing. For retrospectively collected data, the source of collection (medical records, diary log, or participant recall) will be presented.

The analyses will be provided for ABR of treated bleeds and ABR of all bleeds, respectively.

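### SAP 4.2 narrows the protocol's efficacy set with a post-baseline infusion-gap rule, and no ABR or AIR summary is planned on the protocol 9.2 population; the effect can go either way

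*SAP*

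**What the plan says.** Protocol 9.2 defines the efficacy set by consent, nAb-negative status and taking part in follow-up: those "who participated in the prospective data collection phase as part of their usual healthcare setting will be included in the efficacy analysis set". It contains no compliance threshold.

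SAP 4.2 adds that the inclusion and exclusion criteria must be met. Its Note then gives exclusion criterion 2 a numerical form, for anyone followed beyond 120 days. If the longest spell without an infusion entry "represents more than 25% of their follow-up duration will be considered non-compliant with documentation of bleeds and/or prophylaxis replacement therapy administration", that participant "will be excluded from the efficacy analysis set".

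In protocol 4.2, criterion 2 reads only "Lack of participant compliance with documentation of bleeds and/or prophylaxis replacement therapy administration", with no number attached. For non-compliance during the study, protocol 5.2 provides a case-by-case decision: the investigator and sponsor "will determine if a participant should be withdrawn from the study due to a participant's non-compliance".

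On where ABR is reported, SAP 6.1.1 states: "The ABR will be summarized for the efficacy analysis set, the per-protocol analysis set, and the PA#5 analysis set". SAP 6.2.1 handles AIR in the same way. SAP 4.4 builds the per-protocol set from the efficacy set. SAP 4.5 builds the PA#5 set from amendment timing, eligibility and available data, without referring to the gap rule. SAP 4.3 keeps all nAb-negative participants who entered data collection in the safety set, for which no ABR or AIR summary is planned.

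**The concern.** The primary objective is efficacy of prophylaxis in usual care, and protocol 1.2 intends these data as the control for the two gene therapy studies. The rule selects on behaviour observed during follow-up but is presented as an entry criterion. A long stretch without records has at least two causes: a diary that was not kept, or a period in which factor was not infused. The first is a data-quality problem. The second is arguably part of what usual care looks like. The rule treats them alike.

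Selection can also depend on the outcome. The gap is measured between infusion records of any kind, so a treated bleed during a lapse creates a record, shortens the gap and can keep that participant in. Someone with the same lapse and no treated bleed is removed.

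The reported control rate could therefore differ from that of the population the protocol describes, and no planned summary would show by how much.

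**Working it through.** The plan gives no figure for how many participants the rule removes or how they bleed, so there is nothing of its own to reproduce.

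**1. What the rule removes.** Threshold = 0.25 × follow-up, for follow-up above 120 days (SAP 4.2).

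- 121 days: 30.2 days
- 180 days: 45 days
- 365.25 days: 91.3 days
- 730 days: 182.5 days

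At 120 days or less the rule never applies.

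**2. Which summaries it reaches.**

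- Efficacy set: stated.
- Per-protocol set: follows, because it is nested in the efficacy set.
- PA#5 set: not stated. It requires the eligibility criteria, and SAP 4.5 maps it to Groups B2 and B3, which SAP 4.2 lists within the efficacy set. Application is the likely reading.
- Safety set: not affected, but has no ABR or AIR summary.

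**3. Direction for treated bleeds.** Under protocol Appendix 2 and SAP 3.1 a treated bleed needs factor within 72 hours. A stretch without infusion records can therefore hold almost no countable treated bleed, except in about the last 72 hours before the next infusion. Let

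- f = share removed,
- g = share of follow-up lying in the gap,
- k = treated-bleed rate outside the gap, relative to retained participants.

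With all days in the denominator, a removed participant's recorded ABR relative to retained is k(1 − g), so

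all-included mean / retained mean = (1 − f) + f·k·(1 − g).

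The sign changes at k = 1/(1 − g): 1.33 for g = 0.25 and 2.0 for g = 0.50.

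Assumed ranges, none from the documents: f = 2-15%, k = 1-3, g = 0.25-0.50.

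| f | k | g | all / retained | retained against all |
|---|---|---|---|---|
| 10% | 1 | 0.25 | 0.90 + 0.10 × 0.75 = 0.975 | +2.6% |
| 10% | 1 | 0.50 | 0.90 + 0.10 × 0.50 = 0.950 | +5.3% |
| 10% | 2 | 0.25 | 0.90 + 0.10 × 1.50 = 1.050 | −4.8% |
| 10% | 2 | 0.50 | 0.90 + 0.10 × 1.00 = 1.000 | 0% |
| 10% | 3 | 0.25 | 0.90 + 0.10 × 2.25 = 1.125 | −11.1% |
| 15% | 1 | 0.50 | 0.85 + 0.15 × 0.50 = 0.925 | +8.1% |
| 15% | 3 | 0.25 | 0.85 + 0.15 × 2.25 = 1.1875 | −15.8% |

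The last two rows are the extremes over the assumed ranges.

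**4. Dependence on the denominator.** Protocol 9.2.1 counts all days from baseline to end of study. SAP 3.1 counts days while prophylaxis was received and does not say whether gap days are taken out. If they are, the ratio becomes (1 − f) + f·k. At f = 15% and k = 3 this is 0.85 + 0.45 = 1.30, so the retained mean is 1/1.30 − 1 = −23.1%. At k = 1 there is no effect, and below 1, as an incomplete diary could produce, the retained mean is too high.

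**5. AIR.** The same formula applies, with k now the infusion rate outside the gap. At f = 10% and k = 1, with all days counted, the retained mean is 2.6% (g = 0.25) to 5.3% (g = 0.50) above the all-included mean. If gap days leave the denominator, this difference disappears.

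**6. ABR of all bleeds.** Untreated bleeds can be recorded during a gap, so the argument in step 3 does not carry over. Under-recording remains possible.

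**The case against.** The best defence is that the rule protects the estimate. It acts on records, and its own label covers failed documentation. If the diary was not kept, bleeds are probably missing too; SAP 5.3 imputes nothing, so including those participants would pull ABR and AIR down. Prophylaxis is defined in protocol Appendix 2 as a regular, scheduled regimen, and participants must intend to stay on it, so a true stop is arguably outside the question. The rule is also objective, and SAP 6.5.2 already summarizes disposition by analysis set.

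Much of this stands as a reason to keep the rule. It does not supply the missing summary. Disposition counts show that the sets differ in size, but not how many the gap rule removed or what their rates were.

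The defence also rules out several stronger readings. A reader might infer that the rule strips out non-adherent participants and so understates the usual-care ABR. The documents do not say why gaps occur, and step 3 shows the sign can be either. A reader might infer that every ABR analysis is affected, but for PA#5 that is implied, not written. A reader might also infer a procedural breach, since protocol section 9 says "any major modifications of the primary endpoint definitions or their analyses will also be reflected in a protocol amendment" and Amendment 8 has no such rule. The SAP is allowed to modify the plan, its version history presents the text as a clarification, and whether the change is major is a matter of judgement.

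**Conclusion.** The point holds as a departure from the protocol's population with no summary to show its effect. It does not hold as a demonstrated understatement. Under the ranges in the working, with all days counted, the retained-only mean treated ABR falls between 15.8% below and 8.1% above the all-included mean. The share removed, the bleeding rate of those removed and the gap length are all assumptions, and the treatment of gap days in the denominator moves the result further.

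The study tests no hypothesis, so no error rate is at stake; what matters is the control estimate. The documents do not say whether the gene therapy studies will apply the same exclusion, so a carry-over of any bias into those comparisons is possible but not established. This is an inexpensive improvement, not a defect that undermines the study.

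**What to change.** - In SAP 6.1.1 and 6.2.1, add summaries of ABR (treated bleeds and all bleeds) and AIR for all nAb-negative participants who entered data collection. This is the safety analysis set of SAP 4.3 and in substance the protocol 9.2 population. Show them beside the efficacy set, by cohort.
- Report the number removed by the gap rule, with their ABR and AIR.
- State in SAP 4.5 whether the rule applies to the PA#5 set.

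The rule itself can stay. I would not replace it with case-by-case confirmation of gaps: that would put judgement in place of an objective rule in an open-label study, and the documents do not show that reasons for missed infusions are recorded.

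The cost is SAP wording and one extra set of tables from data already collected. The downside is that the added summaries include some poorly documented diaries, which the side-by-side display makes visible.

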4.3. Safety Analysis Set

All enrolled participants (negative for nAb to AAV-Spark100 for the hemophilia B cohort, or negative for nAb to AAV6 for the hemophilia A cohort) who entered the prospective data collection phase will be included in the safety analysis set.

4.4. Per-Protocol Analysis Set

All efficacy analysis set participants who have completed at least 6 months of prospective data collection will be included in the per-protocol analysis set (Groups B1 and B2 in Figure 2).

4.5. Protocol Amendment 5 (PA#5) Analysis Set

All participants enrolled under Protocol Amendment 5 (PA#5) and afterwards, that fulfilled the inclusion/exclusion criteria and who had retrospective and prospective data collected will be included in the protocol amendment 5 analysis set (Groups B2 and B3 in [Figure 2](#)). Of note, the Protocol Amendment 5 analysis set and analyses on retrospective data were originally intended to be applicable to the hemophilia B cohort only, as the hemophilia A cohort had closed enrollment by the time of Protocol Amendment 5 implementation. However, enrollment for the hemophilia A cohort was re-opened in July 2022 to account for attrition following the 1-year temporary halt in Study C3731003 and retrospective data were collected for the newly enrolled hemophilia A participants.

5. GENERAL METHODOLOGY AND CONVENTIONS

The final analysis of each cohort will be performed after the last enrolled participant of the respective cohort completes his end of study visit. The nAb status of AAV-Spark100 and AAV6 endpoints will be evaluated for the hemophilia B and hemophilia A cohorts, respectively. A summary of nAb status of AAV-Spark100 for the hemophilia B cohort will be provided after the last participant's visit within this cohort. A summary of nAb status of AAV6 for the hemophilia A cohort will be provided when all participants from this cohort complete their end of study visit. In addition, when the subsequent study C0371002 or C3731003 reaches an interim analysis timepoint, the data obtained from the appropriate cohort of this study will be used as baseline data for that interim analysis. This may potentially occur earlier than the final analysis for each cohort and/or this study.

The data will be presented separately for each cohort, unless otherwise specified.

5.1. Hypotheses and Decision Rules

There is no hypothesis test planned for this study. Data are collected to facilitate a comparison with post gene therapy efficacy in the subsequent treatment studies (C0371002 or C3731003).

5.2. General Methods

Descriptive statistics will be displayed to summarize data collected in this study. Demographics will be also summarized by region. For numeric variables, the summary statistics include n, mean, standard deviation, median, Q1, Q3, minimum, maximum. For categorical variables, the summary statistics include count and percent of the categories.

5.3. Methods to Manage Missing Data

There is no missing data expected for nAb antibody status, since each participant in the immunity analysis set will have a nAb status reported as defined in [Section 4.1](#).

Missing data for endpoints such as ABR, AIR, total consumption of replacement factor will not be imputed for data summaries or listings. No statistical inference will be made.

For the analysis of safety endpoints, no missing data will be imputed unless otherwise specified.

6. ANALYSES AND SUMMARIES

6.1. Primary Endpoint(s)

6.1.1. Annualized Bleeding Rate

The primary endpoint listed in the protocol is the annualized bleeding rate (ABR; treated and total).

ABR during the prospective data collection period

Annualized bleeding rate during the prospective data collection period will be summarized using descriptive statistics (ie, n, mean, standard deviation, median, Q1, Q3, minimum, maximum) by cohort. The ABR will be summarized for the efficacy analysis set, the per-protocol analysis set, and the PA#5 analysis set.

ABR during the retrospective data collection period

Annualized bleeding rate during the retrospective data collection period will be summarized using descriptive statistics. The ABR will be summarized for the PA#5 analysis set.

ABR from the combined the retrospective and prospective data collection period

Annualized bleeding rate from the combined retrospective and prospective data collection period will be summarized using descriptive statistics. The ABR will be summarized for the PA#5 analysis set.

ABR will be listed in a data listing. For retrospectively collected data, the source of collection (medical records, diary log, or participant recall) will be presented.

The analyses will be provided for ABR of treated bleeds and ABR of all bleeds, respectively.

6.2. Secondary Endpoint(s)

6.2.1. Annualized Infusion Rate and Annualized Total Factor Replacement Therapy Consumption

Both AIR and annualized total factor replacement therapy consumption will be summarized using descriptive statistics. The AIR data will be summarized similarly as ABR as described in Section 6.1.1.

6.2.2. Specific Type of Bleeding Episodes

ABR of bleeding episodes of specific type will be summarized using descriptive statistics by cohort. Bleeding type is not available in retrospective data collection. Thus, the ABR of bleeding episodes of specific type will be summarized for prospectively collected data only. The summary will be presented for the efficacy analysis set and the per-protocol analysis set.

6.3. Other Endpoint(s)

6.3.1. Analysis of nAb Status

AAV-Spark100 nAb status and AAV6 nAb status will be measured from the blood samples collected at the screening visit. NAb status will be summarized as a binary endpoint in a summary table. Additionally, exploratory nAb titers (continuous data) will be included in an individual listing, along with the nAb status.

All participants from the full analysis set (immunity analysis set) will be included in this analysis.

The individual AAV-Spark100 nAb titer will be listed along with the AAV-Spark100 nAb status for each hemophilia B participant by region (Asia, Australia, Europe, Middle East, North America, South America). The study sites included in each region will be finalized after the site selection/participant enrollment decisions are made.

The individual AAV6 nAb titer will be listed along with the AAV6 nAb status for each hemophilia A participant by region. The study sites included in each region will be finalized after the site selection/participant enrollment decisions are made.

The AAV nAb status will be summarized using frequency and percentage by nAb status (positive, negative) overall for all countries combined, and by region. The point estimates of AAV-Spark100 nAb and AAV6 nAb positive rate and the 2-sided 95% confidence intervals (CI) will be provided overall for all countries combined and by region using the exact Clopper-Pearson method. The summary will include the number of nAb positive participants and the number of sampled participants. The nAb status of AAV-Spark100 will be summarized for the hemophilia B cohort and the nAb status of AAV6 will be summarized for the hemophilia A cohort.

6.4. Subset Analyses

No sub-group analyses are planned.

6.5. Baseline and Other Summaries and Analyses

6.5.1. Baseline Summaries

Demographics, medical, surgical and hemophilia history will be summarized using descriptive statistics separately for each cohort. Summaries will be provided overall and by analysis set (safety analysis set, efficacy analysis set, per-protocol analysis set, PA#5 analysis set, respectively). Prior factor (factor IX or factor VIII) treatment will be collected under prior/concomitant medications. These data will be reported in subject-level listings for participants enrolled in the study.

Hemophilia history, including patient exposure categories, disease severity, target joints, current treatment regimen and the type of factor mutation (if known), will be categorically summarized using frequency and percentage for all countries.

6.5.2. Study Conduct and Participant Disposition

Participant evaluation groups will be summarized by end of study participant disposition and by analysis set separately for each cohort (ie, immunity analysis set, safety analysis set, efficacy analysis set, per-protocol analysis set and PA#5 analysis set). Frequency counts will be supplied for participant discontinuation(s) for all countries combined and by region.

A summary of follow-up duration in this study will be provided separately for participants with <180 days of follow-up, participants with \geq 180 days of follow-up, and overall, by analysis set (safety analysis set and efficacy analysis set). Additionally, the number and percentage of participants with a follow-up duration of 1 year or more will be provided.

